Overview of the Design: We propose a two-arm RCT: participants will be randomized to (a) smartphone-based MBSR app (Headspace) or (b) active control (breathing app) for 14 days. Loneliness and quality of social interactions will be assessed using end-of-day diary surveys at baseline (T1) and 14-days after randomization (T2).

Specific Aims and Hypotheses:

Aim 1. *To examine the feasibility and acceptability of providing a mobile health mindfulness meditation training intervention to caregivers with significant caregiving stress and loneliness.*

H1a-b: We expect 80% of caregivers screened will report willingness to use the mindfulness app and at least 75% of participants will complete mindfulness training (at least 80% of expected engagements with the app).

Aim 2. *To examine whether a mobile health mindfulness meditation training intervention reduces loneliness and improves quality of social interactions.*

H2a-b: Participants randomized to mindfulness will demonstrate greater improvements (vs. control) in loneliness (3-item UCLA Loneliness Scale) and quality of social interactions (level of intimacy, involvement and enjoyment during/immediately following a social interaction) via end-of-day diary surveys on REDCap.

Aim 3. *To examine mechanisms whereby mindfulness meditation training reduces loneliness and improves quality of social interactions.*

H3a-b. Participants randomized to mindfulness will demonstrate greater improvements (vs. control) in the mindfulness skills of acceptance through nonjudgment and non-reactivity (Five-Facet Mindfulness Questionnaire [FFMQ]), emotion regulation (Difficulties in Emotion Regulation Scale [DERS]), and self-compassion (Self-Compassion Scale) at follow-up.

H3c (exploratory): Effects of mindfulness skills on loneliness and quality of social interactions will be mediated by improvements in emotion regulation.

II. CHARACTERISTICS OF THE RESEARCH POPULATION

- A. Number of subjects.** We propose a sample size of 50 older adults, enrolling a total of 63 participants over 13 months, using a 20% attrition rate for enrollment estimates.

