- B. Gender of subjects.** Women will be well-represented in this study. Caregivers in the US are more likely to be women (67%); Caregivers are also more likely to be white, non-Hispanic (67%), while 10% are African American and 8% are Hispanic. Using the 2018 Alzheimer's Disease Facts and Figures along with our local demographic distributions, we plan to target 25% minority and 67% women enrollment. We will use the extensive resources in place to meet our minority recruitment goals (including targeting men for enrollment, as they represent the gender minority in the caregiver population).
- C. Age of subjects.** All subjects will be 50 years of age or older.
- D. Racial and ethnic origin.** Subjects will represent the demographics of the local population of subjects at the community organization, as shown in the following table:

Racial Categories	Female	Male	Female	Male	
American Indian/Alaska Native	0	0	0	0	0
Asian	2	1	0	0	3
Native Hawaiian or Other Pacific Islander	0	0	0	0	0
Black or African American	4	2	1	1	8
White	30	14	2	1	47
More than One Race	2	1	1	1	5
Total	38	18	4	3	63

E. Inclusion Criteria (assessed at the HARP screening assessment)

1. Age \geq 50 years old.
2. English speaking.
3. Caregiver for a community-dwelling family member with ADRD, living with (or in close proximity to) family member with dementia.
4. Elevated caregiving distress: above population mean (>11) on 10-item Perceived Stress Scale (PSS-10) and/or at least moderate caregiver strain (score ≥ 5) on the Modified Caregiver Strain Index (MCSI).
5. Social disconnectedness: UCLA Loneliness Scale: Short Form score of ≥ 5 .
6. Access to e-mail in order to complete the e-consent module in REDCap which will be used in this study.

F. Exclusion Criteria (assessed at the HARP screening assessment)

1. Non-English speaking because our primary community partner agency (Lifespan) cannot currently accommodate non-English speaking clients.
2. Those with significant cognitive impairment on a cognitive screening measure at the HARP screening assessment.
3. In order to test the effects of developing mindfulness skills in a novice population, those with a regular systematic mindfulness meditation or related mind-body practice (>2 times per week) will be excluded.

G. Vulnerable Subjects.

Individuals who are 50 years of age and older with social risk factors for poor mental and physical health outcomes will be included. The results of this study will inform

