- E. Randomization.** The Center statistician will be responsible for randomizing all participants. To ensure treatment balance, new participants will be sequentially assigned to receive (a) smartphone-based MBSR app (Headspace) or (b) active control (breathing app) using covariate adaptive randomization, which will take into account covariates (i.e., age and gender) and previous assignment of participants. The statistician will then inform the project coordinator of study condition. In all instances, members of the research team responsible for data collection will remain blind to study condition and the statistician will be the only one with access to the randomization schedule.
- F. Assessments.** Data obtained during the assessments will be obtained specifically for research purposes. Participants will complete the standard STAR baseline and follow-up assessments, with the addition of mindfulness (using the Five-Facet Mindfulness Questionnaire [FFMQ]), emotion regulation (using the Difficulties in Emotion Regulation Scale [DERS]), and Self-Compassion Scale

questionnaires. Loneliness (using the 3-item UCLA Loneliness Scale) and quality of social interactions will be assessed daily using end-of-day diary surveys and all baseline measures will be repeated 3 days after the 14-day intervention.

1. Initial eligibility phone screen: verbal informed consent will be conducted; demographics data will be collected (age, gender, race/ethnicity, education, marital status, living arrangements, caregiver status); and screening instruments will be administered (4-item Perceived Stress Scale, cognitive assessment [Telephone Interview for Cognitive Status; TICS], AUDIT-C, and UCLA Loneliness 3-item scale). Those who do not endorse exclusion criteria for cognition and alcohol abuse will be invited for an initial assessment for further assessment for participation in the study.

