Participants will be characterized at baseline with regards to demographic characteristics, degree of social disconnectedness, caregiver distress, well-being (depressive symptoms, quality of life), cognitive function, and relationship satisfaction with the person they care for. A baseline check of randomness will be conducted for each demographic and outcome variable collected. Mixed-effect linear models (MLMs) will focus on time × condition interactions using end-of-day diary surveys and baseline to follow-up data.

Aim 1. To examine the feasibility and acceptability of providing a mobile health mindfulness meditation training intervention to caregivers with significant caregiving stress and loneliness.

H1a-b: We expect 80% of caregivers screened will report willingness to use the mindfulness app and at least 75% of participants will complete mindfulness training(at least 80% of expected engagements with the app).To assess hypothesis 1, the number of subjects and the number of sessions completed by each will be examined to determine if at least 80% of subjects engage with the app and at least 75% complete a full dose of the intervention.

Aim 2. To examine whether a mobile health mindfulness meditation training intervention reduces loneliness and improves quality of social interactions.

H2a-b: Participants randomized to mindfulness will demonstrate greater improvements (vs. control) in loneliness (3-item UCLA Loneliness Scale) and quality of social interactions (level of intimacy, involvement

and enjoyment during/immediately following a social interaction) via end-of-day diary surveys following procedures by Mote et al.²⁹ To assess hypothesis 2, multilevel mixed-effect linear models (MLMs) will focus on time × condition interactions in end-of-day survey-sampled loneliness and quality of social interactions outcomes (using all available data).

Aim 3. To examine mechanisms whereby mindfulness meditation training reduces loneliness and improves quality of social interactions. H3a-b. Participants randomized to mindfulness will demonstrate greater improvements (vs. control) in the mindfulness skills of acceptance through nonjudgment and non-reactivity (Five-Facet Mindfulness Questionnaire [FFMQ]), emotion regulation (Difficulties in Emotion Regulation Scale [DERS]), and Self-Compassion Scale at follow-up.

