H3c (exploratory): Effects of mindfulness skills on loneliness and quality of social interactions will be mediated by improvements in emotion regulation. To assess hypothesis 3a-b, multilevel mixed-effect linear models (MLMs) will focus on time × condition interactions in mindfulness skills and emotion regulation at follow-up. Exploratory hypothesis 3c examines our belief that the effects of the mindfulness meditation training on loneliness and quality of social interactions are not only direct, but are also indirect, working through emotion regulation. To assess exploratory hypothesis 3c, we will use two simple path analyses using multiple regression, one assessing the link from intervention to emotion regulation to loneliness, and one assessing the link from intervention to emotion regulation quality of social interactions.

V. DATA SAFETY AND DATA MONITORING PLAN

A. Data and Safety Monitoring Plan. The purpose of the Data and Safety Monitoring Plan (DSMP) is to specify the procedures and rationales of the current study to ensure the safety of participants and the validity and integrity of the data. This specifies who will look at the data and review any adverse events, how often, and what they are authorized to do. The use of Data and Safety Monitoring Boards (DSMBs) may be indicated if studies have multiple clinical sites, are blinded (masked), and/or employ particularly high-risk interventions or vulnerable populations. This study on the other hand will be conducted utilizing a low risk intervention in a population of older adults residing independently in the community. Therefore, we have chosen to include a *Data Safety Monitoring Plan Committee* that, while constituted by individuals connected to the study/STAR Center, will systematize monitoring safety issues throughout its duration. The Committee will be led by a designated Safety Officer (SO).

The Principal Investigator (PI) will be responsible for ensuring participants' safety on a daily basis. The DSMP Committee will act in an advisory capacity to the NIA Director and to evaluate the progress of the study, including periodic assessments of data quality and timeliness, participant recruitment, accrual and retention, participant risk versus benefit, performance of trial sites, and other factors that can affect study outcome. The committee will make recommendations to NIA's Director concerning the continuation, modification, or conclusion of the trial.

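### The H3a-b and H2a-b models state no baseline adjustment or common baseline mean: an optional, nearly free gain in precision, firmest for the H3a-b scales

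*Combined protocol and SAP*

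**What the plan says.** Section IV (Data Analysis) tests H2a-b with this sentence: "multilevel mixed-effect linear models (MLMs) will focus on time × condition interactions in end-of-day survey-sampled loneliness and quality of social interactions outcomes". It adds that all available data will be used. For H3a-b it says "multilevel mixed-effect linear models (MLMs) will focus on time × condition interactions in mindfulness skills and emotion regulation at follow-up". That sentence does not mention all available data. It also does not name self-compassion, although the hypothesis includes it.

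No section lists the fixed effects, random effects or covariance structure. None names a baseline covariate or a common baseline mean. Apart from the interaction, the analysis section uses baseline values in two ways: to describe the participants, including their degree of social disconnectedness, and for a balance check: "A baseline check of randomness will be conducted for each demographic and outcome variable collected". No consequence of that check for the model is stated.

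Section III.E assigns by "covariate adaptive randomization, which will take into account covariates (i.e., age and gender) and previous assignment of participants", so baseline outcome scores are not balanced by design. The FFMQ, DERS and Self-Compassion Scale are collected at the initial assessment (III.F, item 2f).

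The diary schedule is given in two ways. The opening of III.F has loneliness and interaction quality measured every day. Item 3 of III.F has three days before and three days after the intervention.

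Exploratory H3c has its own method ("we will use two simple path analyses using multiple regression") and is outside this point.

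**The concern.** A time × condition interaction with free baseline means subtracts the whole of each arm's baseline mean from its follow-up mean. When baseline and follow-up are imperfectly correlated, this usually subtracts too much, and chance differences at baseline enter the estimate as noise.

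Baseline outcome scores are left to chance here and the trial is small. With 63 baselines split 31 and 32, the arms differ at baseline with a standard error of √(1/31 + 1/32) = 0.25 SD. With equal SDs, a chance difference of that size moves the free-baseline contrast by 0.25 × (1 − correlation): 0.13 SD at correlation 0.5 and 0.05 SD at 0.8.

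The plan gives no power calculation for Aims 2 and 3. What they can usefully deliver is an effect estimate with its interval, so the width of that interval is what is at stake.

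**Working it through.** **The plan's own figure.** Section II.A aims for 50 participants, "enrolling a total of 63 participants over 13 months, using a 20% attrition rate for enrollment estimates". 50 / (1 − 0.20) = 62.5, rounded up to 63, which agrees. No effect size, SD, correlation or power is given, so the 50 itself cannot be reproduced.

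**Inputs.** From the documents: two arms, 50 completers, 63 enrolled, one pre and one post assessment for the H3a-b scales. Assumed: equal allocation (25 completers per arm, 31 + 32 baselines), follow-up SD 1, baseline SD *q*, pre-post correlation *ρ*, follow-ups missing at random.

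**Formulas (variance of the arm contrast).**
- Free baseline, complete data: [(1 − ρ²) + (q − ρ)²] × 2/25
- Free baseline, 63 baselines and 50 follow-ups: (1 − ρ²) × 2/25 + (q − ρ)² × (1/31 + 1/32)
- Common baseline mean: (1 − ρ²) × 2/25 × (1 + 1/46), where the last factor is the small-sample cost of estimating the baseline slope

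The term (q − ρ)² is never negative. A common mean therefore loses only through the factor of about 2%, and only when q is close to ρ or ρ is close to 1.

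**Worked case, q = 1, ρ = 0.6.** Complete data: free = (0.64 + 0.16) × 0.08 = 0.0640; common = 0.64 × 0.08 × 1.0217 = 0.0523; ratio 0.817. With 63/50: free = 0.0512 + 0.16 × 0.0635 = 0.0614; ratio 0.853.

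**Variance ratio, common mean / free baseline.** Each cell gives complete data (formula), then 63/50 (simulated, 40,000 runs, maximum likelihood with unstructured covariance).

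| ρ | q = 1.0 | q = 0.9 | q = 0.8 |
|---|---|---|---|
| 0.5 | 0.766 / 0.803 | 0.842 / 0.875 | 0.912 / 0.929 |
| 0.6 | 0.817 / 0.856 | 0.896 / 0.919 | 0.962 / 0.971 |
| 0.7 | 0.868 / 0.897 | 0.947 / 0.962 | 1.002 / 1.001 |
| 0.8 | 0.920 / 0.939 | 0.994 / 0.994 | 1.022 / 1.016 |
| 0.875 | 0.958 / 0.969 | 1.019 / 1.012 | 0.998 / 0.999 |

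The 63/50 formula agrees with the simulation to within about 0.01. The simulated type I error of the common-mean contrast was 4.8-5.1%.

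**H3a-b scales, ρ 0.5-0.8.** With 25 completers per arm, the variance is 8-23% lower at q = 1 and 1-16% lower at q = 0.9. If all 63 baselines enter, it is about 6-20% and 0-12% lower.

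**95% half-width, 63/50 (1.96 × square root of the variance).**
- q = 1, ρ = 0.6: 0.49 to 0.45 SD
- q = 1, ρ = 0.8: 0.35 to 0.34 SD
- q = 0.9, ρ = 0.6: 0.47 to 0.45 SD
- q = 0.9, ρ = 0.8: 0.34 to 0.34 SD

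**Diary outcomes, if the schedule is three days before and three after.** With an assumed 50-70% of daily variance between persons and a latent pre-post correlation of 0.8-1.0, the 3-day means correlate at 0.60-0.875.
- Interaction quality is not an eligibility score. At q = 1 with complete data, the variance is 4-18% lower.
- Loneliness is an eligibility score ("UCLA Loneliness Scale: Short Form score of ≥ 5"), which may narrow its baseline spread. At q = 0.9 the range is 10% lower to 2% higher; at q = 0.8 it is 4% lower to 2% higher.
- A separate selection model for loneliness, with its own assumed inputs, gave q 0.83-0.96, ρ 0.47-0.78 and ratios of 0.83-0.99. It allows lower correlations, so it is more favourable. The less favourable range is the safer one to quote.

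**The case against.** The strongest reply is that nothing in the plan is wrong. Under randomisation the difference in change is unbiased and its test is valid. The model terms are not listed, so a common baseline mean may already be intended. In a pilot seeking initial evidence, preferring one valid estimator to another is a refinement. All of this stands, and it is why the point is optional.

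The gain is also uneven. It may vanish for loneliness, and at correlation 0.8 the H3a-b interval hardly changes even with equal SDs. The 0.13 SD shift is likewise an equal-SD figure. At q = 0.9 and ρ 0.60-0.875, the range used for loneliness, 0.25 × (q − ρ) is about 0.01-0.08 SD. This stands too.

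The diary figures depend on a pre/post schedule that the opening of III.F does not support. If diaries ran every day, time × condition could mean a trajectory and these figures would not apply. Hence the fix for the diaries is conditional.

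A reader might infer three stronger points that the documents do not support:
- *That the plan ignores baseline or gives a biased answer.* Baseline enters through the interaction, the description of the sample and the balance check, and the contrast is unbiased.
- *That the 63-baseline figures describe the planned H3a-b analysis.* Use of all available data is stated for H2 only. For H3a-b it is an assumption, though a common one for mixed models.
- *That about 20% of variance is being lost throughout.* That is the favourable end: equal SDs and correlation 0.5.

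**Conclusion.** The point holds as a missed gain in precision. It is firmest for the H3a-b scales, which are not eligibility scores and are measured once before and once after. There, across the assumed correlations and SD ratios of 0.9-1.0, the variance of the arm contrast falls by 1-23% with 25 completers per arm. For diary interaction quality the gain is modest and conditional on the schedule. For diary loneliness it may be nil.

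The largest loss in any case examined is about 2% of variance. That small cost against a likely gain is the reason to make the change, but no validity problem compels it. All sizes rest on assumed SDs, correlations and equal allocation.

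**What to change.** **FFMQ, DERS and Self-Compassion Scale.** Keep the mixed model. State that it contains time and time × condition with no condition main effect, so that both arms share one baseline mean, and an unstructured pre/post covariance. Adjusting follow-up for the baseline score serves the same purpose. Name self-compassion in the H3a-b model sentence and say whether all available data are used. Report the arm difference at follow-up with its 95% CI.

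**Diary loneliness and interaction quality.** First settle two things:
1. Reconcile the daily schedule in the opening of III.F with the three-days-before-and-after schedule in item 3.
2. Confirm that the baseline diaries precede randomisation. The design overview calls them baseline; item 3 says only that they come before the intervention.

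If the pre/post schedule stands and the baseline diaries precede randomisation, apply the same constraint, with time coded pre/post and a participant-by-phase effect. If the diaries do not precede randomisation, do not impose the common mean on them.

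H3c needs no change.

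**Cost.** For the H3a-b scales, a sentence or two in the analysis section and no new data. For the diaries, the two clarifications as well. The statistical downside is up to about 2% more variance when the baseline slope is near 1, for example SD ratio 0.8 with correlation 0.8. Write the choice down before outcomes are seen, so that the balance check does not prompt it.

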2. Initial assessment: A Clinical Research Coordinator (CRC) will conduct the interview via telephone or Zoom. The CRC will explain the study purpose and procedures as well as potential eligibility for pilot studies. The process of obtaining informed consent involves completing procedures to ensure the potential subject has the capacity to provide informed consent (see **C. Process of Consent** for more detail regarding the informed consent). The CRC will obtain E-consent for participation via REDCAP. Subjects will also receive a brief orientation to the end-of-day diary surveys via REDCap. Next, the CRC will administer the STAR Core Battery that assesses domains central to the Center's scientific mission (see below):
 - a. Social connectedness: the *UCLA Loneliness Scale*, version 3, has demonstrated excellent internal consistency, test re-test reliability, and construct validity (associations with social support, social network size),⁶ including with older adults^{6,7} and is sensitive to change;⁸ the *Berkman-Syme Social Network Index*⁹ measures social integration and has strong predictive validity for morbidity, mortality;¹⁰⁻¹² the *Interpersonal Support Evaluation List*¹³ assesses three components of social support: tangible, belonging, and self-esteem; *Unidimensional Relationship Closeness Scale*¹⁴ assesses quality of relationship between participant and family member and has demonstrated valid scores across several relationship types, including spouses and other family members; *PROMIS Social Functioning Computerized Adaptive Tests*¹⁵ which provide age-normed scores of social functioning.
 - b. Caregiving: *Montgomery Borgatta Caregiver Burden Scale*¹⁶ assess objective burden, subjective burden and subjective stress burden; *Modified Cornell Services Index*¹⁷ assesses formal & informal health/ social services usage, including caregiver support services; Objective Caregiver Burden subscale of the Caregiver Burden Scale¹⁸ will assess type and extent of current caregiving activities.

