 - c. Health indicators: *WHO Disability Assessment Schedule* (WHODAS 2.0)¹⁹ measures functioning in 6 domains (cognition, mobility, ADLs, IADLs, social functioning, social participation); *Medical conditions and medications*²⁰ will be assessed with a checklist of self-reported medical conditions derived from the Minimum Data Set Version 2.0.; *Pittsburgh Sleep Quality Index* (PSQI)²¹ differentiates poor from good sleep by assessing domains of sleep quality and disruptions; *Fatigue and pain* will be assessed with PROMIS computer adaptive tests;¹⁵ the *Montreal Cognitive Assessment* (MOCA)²² has alternate forms to prevent practice effects with repeat administration to assess changes in cognition over time.

- d. Well-being indicators: *WHOQOL-BREF*²³ is a 36-item measure of several domains of health related quality of life; *PROMIS Depression and Anxiety Computerized Adaptive Tests* are sensitive to detecting clinical levels of psychological distress;
- e. Mechanisms of behavior/social connectedness change. *Interpersonal Needs Questionnaire (INQ)*^{24,25} measures unmet psychological needs for belonging and relatedness (as conceptualized by Self-Determination Theory) and has strong construct and predictive validity for negative health outcomes;²⁴ the *Perceived Competence Scale* and *Perceived Autonomy Scale*^{26,27} measure the other psychological needs posited by Self-Determination Theory (autonomy, competence); the *PSS-10*²⁸ for perceived stress.
- f. In addition to STAR Core Battery assessments, participants will also be assessed for mindfulness skills and emotion dysregulation. The *Five-Facet Mindfulness Questionnaire (FFMQ)* measures five factors that represent mindfulness as it is currently conceptualized: observing, describing, acting with awareness, non-judging of inner experience, and non-reactivity to inner experience; the *Self-Compassion Scale* measures self-compassion in six domains: self-kindness, self-judgment, common humanity, isolation, mindfulness, and over-identified; the *Difficulties in Emotion Regulation Scale (DERS)* measures emotion dysregulation in six domains: nonacceptance of emotional responses, difficulties engaging in goal directed behavior, impulse control difficulties, lack of emotional awareness, limited access to emotion regulation strategies, and lack of emotional clarity.

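### The exploratory H3c path analyses name no baseline terms, and DERS is not measured before the outcome window, so the indirect effect should be baseline-adjusted and reported as an association

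*Combined protocol and SAP*

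**What the plan says.** Section IV (Data Analysis), Aim 3, tests H3c by regression: "we will use two simple path analyses using multiple regression, one assessing the link from intervention to emotion regulation to loneliness". A second path analysis puts quality of social interactions in place of loneliness. Neither description names a covariate, a baseline value, a change score, or a test or interval for the indirect effect.

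The one-line hypothesis, in Section I and again in Section IV, reads "Effects of mindfulness skills on loneliness and quality of social interactions will be mediated by improvements in emotion regulation". The explanatory sentence that follows in Section IV takes the training as the exposure: "the mindfulness meditation training on loneliness and quality of social interactions are not only direct, but are also indirect, working through emotion regulation".

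DERS is collected twice. At the initial assessment (III.F, item 2f), "participants will also be assessed for mindfulness skills and emotion dysregulation". After randomisation, III.F states that "all baseline measures will be repeated 3 days after the 14-day intervention". The diaries that carry loneliness and interaction quality cover 3 days before and 3 days after the intervention (III.F, item 3).

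The opening of Section IV describes the mixed models as "using end-of-day diary surveys and baseline to follow-up data". The path-analysis text makes no similar statement.

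**The concern.** An indirect effect is the product of two links: intervention to DERS, and DERS to outcome given intervention. Only the first is protected by randomisation. People who regulate emotion poorly may also be lonelier for lasting reasons, and an event during follow-up can worsen both. Either produces a DERS-to-outcome association without any effect of DERS. If the app does move DERS, as H3a-b predicts, both links can then be significant and the result can look like mediation.

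Timing adds to this. With DERS measured no earlier than the outcome, the data cannot separate DERS acting on loneliness from loneliness acting on DERS. Aim 3 is framed as a study of mechanisms, and the plan states no limit on how the indirect effect may be read. What is at stake is the mechanism statement, not the randomised comparisons.

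**Working it through.** **Figures in the plan.** The plan gives no effect size, correlation or power for H3c. Its one design calculation is enrolment (Section II.A): 50 / (1 - 0.20) = 62.5, rounded up to 63, which reproduces. The check below uses the 50.

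**Timing.** Number the intervention days 1 to 14 (my numbering). The post-intervention diaries fall on about days 15-17 and the follow-up DERS on about day 17. The design overview puts T2 at 14 days after randomisation, and III.F also speaks of daily diaries. Either reading moves outcome data earlier, not later. On no reading does a post-randomisation DERS precede the outcome window.

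**Models.** X is arm, M is DERS, Y is the outcome; 0 is baseline and 1 is follow-up.
- Link a: M1 = constant + a·X + error
- Link b: Y1 = constant + c·X + b·M1 + error
- Indirect effect: a·b

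Three versions were compared: follow-up scores only; the same with M0 and Y0 in both regressions; and change scores for M and Y.

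**Assumed inputs (none is in the documents).** 25 per arm, two-sided 5%, a = 0.5 SD, true b = 0, baseline DERS-outcome correlation r = 0.3, 0.4 or 0.5, stability s = 0.6, 0.7 or 0.8, follow-up residual correlation q = 0 or 0.3. Two data models (stable trait, autoregressive) give 2 × 2 × 9 = 36 settings.

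**Expected false b, by algebra (unit variances).**
- No baseline terms, stable trait: r + q(1 - s). With r = 0.5, s = 0.6, q = 0.3: 0.5 + 0.3 × 0.4 = 0.62.
- No baseline terms, autoregressive: s²r + q(1 - s²). With q = 0 it runs from 0.36 × 0.3 = 0.11 to 0.64 × 0.5 = 0.32.
- Covariates, autoregressive: q. The baseline part goes, and a residual correlation of 0.3 stays in full.
- Change scores, stable trait: the trait cancels, leaving q(1 - s) / [2(1 - s)] = q/2, which is 0.15 when q = 0.3.

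**Simulated false rates.** 20,000 runs per setting; minimum to maximum over the nine r-s combinations. Order in each cell: no baseline terms / covariates / change scores.

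| Setting | Both links significant | DERS-to-outcome link alone |
|---|---|---|
| Stable trait, q = 0 | 22-40% / 4-14% / 2-4% | 55-97% / 6-24% / 5% |
| Stable trait, q = 0.3 | 29-41% / 23-46% / 8-14% | 73-100% / 28-78% / 17-18% |
| Autoregressive, q = 0 | 5-25% / 3-4% / 3-5% | 11-63% / 5% / 5-11% |
| Autoregressive, q = 0.3 | 22-36% / 30-44% / 27-49% | 56-88% / 54-55% / 57-68% |

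Covariates lower the false DERS-to-outcome rate in 36 of 36 settings and the false joint rate in 27 of 36. The 9 where the joint rate rises all have q = 0.3: 8 autoregressive (the worst goes from 22% to 43% at r = 0.3, s = 0.8) and 1 stable-trait (41% to 46%). It rises because the real effect on DERS is detected more often: 55-83% with covariates, 40-42% without, 48-79% with change scores.

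**Second check, interval for a·b.** Autoregressive, baseline slope 0.6, 3,000 runs, baseline correlation 0.3, 0.5 and 0.7, q = 0. Without baselines the mean false indirect effect is 0.055, 0.091 and 0.126 (expected 0.5 × 0.36 × r = 0.054, 0.090 and 0.126), and the interval excludes zero in 4.0%, 9.3% and 17.0% of runs. With both baselines the mean is 0.00 and the rate about 2.7%. With q = 0.3 and correlation 0.5, the means are 0.188 and 0.153, and about 32% of intervals exclude zero either way. If the outcome drives DERS instead, 11-23% exclude zero without baselines and 14-31% with them.

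**The case against.** H3c is labelled exploratory, in a pilot of 50, and the plan promises no causal conclusion beyond examining mechanisms. The phrase "will be mediated by improvements in emotion regulation" may hint at change scores, which have much lower false rates than covariates under stable traits. The case for covariates rests partly on better detection of the effect on DERS, which H3a-b already tests by mixed models. Covariates can also raise the false joint rate. The size of the problem depends wholly on assumed inputs, and no SAP wording can change when DERS is measured.

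Most of this stands. It limits the point to an optional improvement, supports change scores as a companion analysis, and makes the association label the essential part. It does not show that baseline enters the path analyses, because the text never says so.

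Two stronger readings are tempting. A reader might infer that the loneliness outcome is undecided, because the interview battery includes a UCLA scale ("version 3, has demonstrated excellent internal consistency, test re-test reliability, and construct validity"). The documents do not support this: the design overview, III.A, III.F item 3 and H2a-b all tie loneliness to the diaries, as the 3-item score wherever the scale is named, and the interview scale is attached to no hypothesis. A reader might also infer that H3c holds two competing hypotheses, one left untested. Section IV itself explains H3c as an effect of the training, and both models start from the intervention. Only the one-line label is loose.

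**Conclusion.** The point holds. As written, the H3c regressions can yield an apparent indirect effect when DERS has no effect on the outcome, and the measurement schedule cannot rule this out. Under the assumed inputs, the false joint rate without baseline terms runs from 5% to 41%. These figures illustrate the mechanism and are not estimates for this trial. The second check gives only 4-17% without residual correlation, so the upper end should not be quoted as the size of the problem.

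Baseline covariates remove the part due to measured baseline differences. They do not remove shared causes after baseline, reverse order, or the trait differences that a single baseline measures imperfectly. It would be wrong to conclude that adjustment makes the indirect effect causal. It would be equally wrong to conclude that the randomised effects on DERS or on the outcome are compromised; those keep their causal reading. This is a cheap improvement to an exploratory analysis, not a flaw in the trial's main comparison.

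**What to change.** In Section IV, Aim 3:

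1. State that both path analyses use follow-up DERS and the follow-up diary outcome, with baseline DERS and the baseline value of the same diary outcome as covariates in both regressions. Pre-specify a change-score version as a sensitivity analysis.
2. State that the indirect effect is reported with a 95% confidence interval, its method named in advance, as an exploratory association and not as evidence of mediation. Add that the randomised effects on DERS and on the outcome are interpreted causally.
3. Minor: change the one-line H3c label, in Sections I and IV, so that its exposure is the intervention, as modelled.

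The baseline values are already collected, so no visit or form is added. The price is two degrees of freedom per regression (with 50 analysed, residual degrees of freedom go from 48 to 46 for link a and from 47 to 45 for link b) and a more modest statement on mechanism.
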